Appendix A: O₂VERLAP Enrollment and Randomization Coach Workflow

Appendix B: Oxygen Adherence Monitoring

[figure not shown]
Appendix C: Respiratory Therapist Scripts and Peer Coach Scripts

Appendix D: DatStat Security and Compliance

[figure not shown]
Enrollment Workflow

Randomization
Outcome: RC Arm

Randomization Outcome: PC Arm

Appendix B: Oxygen Adherence Monitoring

This subset of the studies participants (i.e. oxygen users) will be asked to answer the following questions at Baseline. Subsequent reporting on oxygen adherence at 30-day, 60-day and 90-day follow-ups is very similar but will also require updates on changes to the ongoing oxygen prescriptions listed in the system and adding any new oxygen prescriptions.

1. Baseline Assessment:

- a. Oxygen Equipment (multiple-choice which allows multiple selections)
 - i. stationary concentrator
 - ii. portable concentrators
 - iii. oxygen tanks
 - iv. home fill system with tanks
 - v. liquid oxygen reservoir with portable system
 - vi. other [include text box with unlimited word count]
 - vii. Would you like to provide any additional information or explanations relating to your oxygen equipment which were not covered? [include text box with unlimited word count]
 - viii. Please indicate at what point during the day you use each of the above selected Oxygen Equipment. Please list each selected item above and give a brief description of the time of day or activity which requires use of this equipment. [include text box with unlimited word count]
- b. Additionally, for any item chosen above there should then appear a multiple-choice selection, allowing multiple selections, which asks a participant to indicate at what time of day they use this equipment.

Example

“Portable Concentrator” selected

What time of day do you typically use this equipment?

- i. Morning
- ii. Afternoon
- iii. Evening
- iv. During Sleep

What activities do you use this equipment during?

- i. I use this while sitting in place.
- ii. I use this when walking long distances only (i.e. to walk a dog, to run errands, to go to the grocery store, to enjoy an afternoon outside).
- iii. I use this when walking long or short distances (i.e. to walk a dog, to run errands, to go to the grocery store, to enjoy an afternoon outside, or to simply go to the bathroom, or while you stand to make lunch, or to go upstairs)
- iv. I use this when exercising only.
- v. I use this during sleep.

- c. [for each equipment listed above, it should have a corresponding “Oxygen prescription” survey]

"[insert relevant equipment name AND there should also be an option for "other" to report on additional equipment not classified above] Oxygen Prescription"

- i. dose
- ii. duration of use
- iii. date of original prescription
- iv. other [include text box with unlimited word count]
- v. Would you like to provide any additional information or explanations relating to this oxygen prescription which were not covered? [include text box with unlimited word count]

d. Typical adherence in last 7-days (self-assessment of percentage of time they complied with oxygen prescription; this section should autopopulate sections based on the type of equipment the participant reported using in the above question. For example, stationary concentrator should have its own section, home fill systems with tanks should have its own section)
[the response option should show Sunday-Saturday, with each having a corresponding text box that only allows numeric values that are two-digits long- this should show a total at the bottom of the page indicating the total amount of time the participant is self-reporting as using oxygen that week]

Please report your use of your [populate type of Equipment being reported based on initial Oxygen Equipment question AND provide an "other" option]. Please report your use of this equipment at rest, as well as when you are using your oxygen moving around. Please also include the number of hours this equipment is used while you are sleeping.

- i. Sunday: [Answer: text box allowing only two-digit numeric values]
- ii. Monday: [Answer: text box allowing only two-digit numeric values]
- iii. Tuesday: [Answer: text box allowing only two-digit numeric values]
- iv. Wednesday: [Answer: text box allowing only two-digit numeric values]
- v. Thursday: [Answer: text box allowing only two-digit numeric values]
- vi. Friday: [Answer: text box allowing only two-digit numeric values]
- vii. Saturday: [Answer: text box allowing only two-digit numeric values]

TOTAL HOURS: [values should add up and be divided by 168 hours in a week, and then multiplied by 100 to give percentage] e.g. if someone reports only using all oxygen equipment for a total of 24 hours this week, we would have $(24/168)*100=14.28\%$.

Now, please report the total number of hours you used oxygen during sleep ONLY (on average) while sleeping: [Answer: text box allowing only two-digit numeric values]

Additionally, please provide any comments or explanations of oxygen use for the week which have not yet been covered; for example, did anything prevent you from using your oxygen? Have you run into any other difficulties using your oxygen as prescribed? Did you find that your oxygen was particularly useful during a given activity? Is there anything else you would like to share about your use of oxygen this week? [include text box with unlimited word count to allow participants to provide additional insights to their adherence patterns for the week being self-reported]

2. Subsequent 30-day, 60-day and 90-day assessments:

- a. The participant should be asked "Have any of your oxygen prescriptions changed since you last reported your weekly oxygen use?"
 - i. "Yes, one or more of my oxygen prescriptions have changed."
 - ii. "No, my oxygen prescriptions are the same as they were when I volunteered to participate in this research.".

If the answer is NO then the participant should be required to fill out items 1b, 1c and 1d listed above.

However, if a participant indicates "Yes.." one or more prescriptions has changed then the answer should populate based on their initial selection in item 1a. above; they should be able to select from their currently identified prescriptions.

Please indicate the type of update required:

- i. I need to update this oxygen prescription.
- ii. I no longer use this oxygen prescription.
- iii. I would like to add a new oxygen prescription.

If they choose i. or iii, the corresponding items 1b, 1c and 1d for that prescription should appear to be updated along with all other, current, prescriptions previously reported in item 1a.

If they choose ii. the portal should show their current list of other, current, prescriptions previously reported in item 1a. They should be asked to self-report on the current oxygen prescriptions by filling out items 1b, 1c and 1d for each oxygen prescription. It should also indicate that [insert old equipment and prescription] has been removed and ask the participant to enter the date which this prescription was discontinued.

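### Oxygen item 1d is described as compliance but computed as share of the week, oxygen follow-up is timed three ways, and, separately, Table 1.0 gives the follow-up surveys to one arm only

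*Combined protocol and SAP*

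**What the plan says.** **Oxygen item.** Appendix B, item 1d, introduces the seven-day figure as a "self-assessment of percentage of time they complied with oxygen prescription". The same item describes the total at the foot of the page as "indicating the total amount of time the participant is self-reporting as using oxygen that week", and the calculation rule is that "values should add up and be divided by 168 hours in a week, and then multiplied by 100 to give percentage". Prescribed hours do not enter the rule.

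Entry is by device: "stationary concentrator should have its own section, home fill systems with tanks should have its own section". The worked example, however, starts from the case "if someone reports only using all oxygen equipment for a total of 24 hours this week". Each day has a "text box that only allows numeric values that are two-digits long", with no stated maximum of 24 h.

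Item 1c asks for "duration of use" under each equipment's prescription, without a unit. A further question asks participants to "report the total number of hours you used oxygen during sleep ONLY (on average) while sleeping".

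**Oxygen follow-up times.** The protocol section on oxygen prescription and self-reported adherence gives baseline, 6 weeks and 12 weeks. Table 1.0 has rows at baseline, 30 days and 12 weeks. Appendix B (introduction and item 2) gives 30, 60 and 90 days after baseline.

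**Surveys.** Table 1.0 marks the 6-week row (FOSQ, CAT, ESS, PSQI, PROMIS) and the 12-week row as proactive care arm only. Study Secondary Aims compares the two arms on change from baseline to both times. Payment for Participation pays participants at 6 and 12 weeks without naming an arm.

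**The concern.** A percentage presented as adherence should reach 100% when the prescription is fully followed. This one does so only for continuous oxygen. The form itself expects less than that: item 1b offers use during sleep only and use during exercise only. The Background quotes long-term oxygen adherence of 45% to 70%, so a reader could set the item 1d figure beside that range and take a fully compliant night-time user for a poor one.

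The three sets of follow-up times cannot all be carried out as written. They differ in number (two or three) as well as in timing, and the protocol body refers to Appendix B for detail that then contradicts it.

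The survey rows are a different matter from the oxygen form. They concern the data for Aim 2, which needs follow-up scores from both arms.

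**Working it through.** **1. The plan's own figure.** 24/168 × 100 = 14.2857. The printed 14.28% is this value truncated (14.29 if rounded), so the example follows its formula.

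**2. Description against formula.** Let p be prescribed hours per day and H the hours reported in the week.

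- Form: H/168 × 100
- Hours used relative to hours prescribed: H/(7p) × 100
- Relation: H/168 = (p/24) × H/(7p), so the two are equal only when p = 24.

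The documents give no prescribed hours; the values of p below are assumptions.

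| p (h/day) | Form's figure at full compliance | The example's 24 h relative to prescribed hours |
|---|---|---|
| 6 | 42/168 = 25.0% | 24/42 = 57.1% |
| 8 | 56/168 = 33.3% | 24/56 = 42.9% |
| 12 | 84/168 = 50.0% | 24/84 = 28.6% |
| 16 | 112/168 = 66.7% | 24/112 = 21.4% |
| 24 | 168/168 = 100% | 24/168 = 14.3% |

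For one person with an unchanged prescription, p/24 is constant, so relative change over time is preserved. The absolute level and comparisons between people are not.

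**3. Pooling.** Assume 8 h/night on one device and 6 h/day on another. By section the form shows 56/168 = 33.3% and 42/168 = 25.0%; pooled it shows 98/168 = 58.3%. Only the pooled figure is the participant's share of the week, and only if the hours do not overlap.

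**4. Range.** Seven boxes that accept 99 allow 7 × 99 = 693 h, and 693/168 = 412.5%. An entry of 24 h/day on one device and 6 h/day on another pools to (168 + 42)/168 = 125.0%. These show that a limit is missing; they do not predict what participants will enter.

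**5. Follow-up times**, counted from one start day (assumed):

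| Place | Follow-up days |
|---|---|
| Protocol body | 42, 84 |
| Table 1.0 | 30, 84 |
| Appendix B | 30, 60, 90 |

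Day 42 is 42 − 30 = 12 days after day 30 and 60 − 42 = 18 days before day 60. Day 84 is 90 − 84 = 6 days before day 90. Table 1.0 attaches a one-week window to the survey rows but none to the oxygen rows. A one-week window would in any case not bridge the 12-day gap.

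**6. Survey rows.** Half of 330 is 165. If Table 1.0 were followed literally, 165 reactive-arm participants would have baseline scores only, and the two-arm comparison of change could not be made at either time.

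**The case against.** The compliance wording is a parenthetical note to whoever builds the form. The participant is asked about use, the computed line is labelled as total hours, and a second note calls it time on oxygen. Other items help to interpret the hours: item 1b (time of day and activity), item 1c, the sleep-only question, and the respiratory therapist's script, which asks about hours of use and reasons for not following the prescription. This limits the harm, but the item's description and its formula still disagree.

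A reader might infer that the level of pooling is not stated at all. The documents do not support that. The worked example counts all equipment and the page total is described for the participant, so both point to one pooled total. What remains is that this sits awkwardly with separate sections per device, and that overlapping hours have no rule. The missing upper limit is a range check and no more.

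A reader might also infer that the plan leaves reactive-arm outcomes uncollected. That goes too far. Payments at 6 and 12 weeks are not restricted by arm, and the analysis compares both arms. The same table also marks the baseline CPAP upload as proactive arm only, although the Randomization section requires it of everyone before allocation. The survey entries therefore look clerical. Table 1.0 is still the activity schedule and contradicts the analysis, so the rows need correcting.

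**Conclusion.** All three inconsistencies stand, with different weights.

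- **Oxygen figure and oxygen follow-up times: small.** The percentage cannot be read as adherence for anyone prescribed less than 24 h/day, and staff cannot tell which oxygen follow-ups to run. The size shown (for example 33.3% at full compliance) rests on assumed prescribed hours, and the number of oxygen users is not given. Oxygen adherence is in none of the aims and none of the planned analyses, so the text gives no ground for inferring that a primary or secondary conclusion changes through this variable. Nor is there an arithmetic error in the worked example.
- **Survey rows: separate and more consequential.** Read literally, they remove all follow-up scores for 165 of 330 participants from the Aim 2 comparison. The likelier reading is a table error. This point should be judged on its own and lends no weight to the oxygen form.

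**What to change.** 1. **Oxygen figure.** Relabel hours/168 as *share of week on oxygen*. Compute it once per participant across all equipment. Limit each daily entry to 0-24 h and query any day whose sum across equipment exceeds 24 h.
2. **Only if an adherence percentage is wanted.** Give the existing duration field in item 1c a unit (prescribed hours per day) and derive one prescribed-hours denominator per participant, so that two devices serving the same prescribed hours are not counted twice. Report 100 × weekly hours reported / weekly hours prescribed, described as hours used relative to hours prescribed, because extra hours on one day can offset missed hours on another. Record *not calculable* where no fixed hours are prescribed, such as exercise-only use.
3. **Oxygen follow-up times.** Reconcile the protocol body, Table 1.0 and Appendix B to one set of assessment times, with any window, before data collection. Six and 12 weeks would coincide with the surveys and the payments.
4. **Survey rows.** Correct the 6- and 12-week rows of Table 1.0 so that both arms complete the surveys, in line with Study Secondary Aims.

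The cost is one label, one pooled total with a range check, one unit on an existing field, and wording changes in three places plus two table rows. Participants without fixed prescribed hours would have no adherence percentage. If the portal cannot be changed, the share of the week can be recomputed at analysis from the daily entries, but overlapping or impossible entries could then only be flagged, not queried.

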Appendix C: Respiratory Therapist Scripts and Peer Coach Scripts

Respiratory Therapist Scripts

PAP Questions:

These questions should be asked each time a Respiratory Therapist coach interacts with a participant.

After each interaction you should fill out a communications tracking form to document the conversation. When you complete your communications tracking form in the study portal, the participant will then be triggered to fill out a communication satisfaction survey; they will be asked to rate the conversation from 1-10 (i.e. 1 being not satisfied at all and 10 being completely satisfied) and will also be prompted to provide feedback. Should a participant rate any study communication less than seven, the team will be prompted to reach back out to that participant to reconcile any miscommunications or perceived inefficiencies.

“Hi, my name is _____, I am one of the Respiratory Therapists which will be acting as a Peer Coach during the study. I should first say that any advice that is given throughout the study does not replace regular visits with your healthcare providers, in fact, depending on your questions we may recommend you continue a conversation or topic with your healthcare provider so that you can receive clinical support.”

“Do you have any questions about that?” [Answer questions, clarify.]

“Let’s get started reviewing some of your current PAP device settings and habits. I am going to ask you some general questions about how you currently use your PAP device. There are no right or wrong answers! We want to help as much as possible. Ok, let’s get started.”

- 1) Are you wearing your PAP device?*
 - 1a. If so is it every night? How many hours?*
- 2) Do you experience leaking, skin irritation, nasal or mouth dryness, or pressure sores from your mask?
 - 2a. If so what do you do about it?
- 3) How are you cleaning and disinfecting your PAP unit and associated tubing?
- 4) How do you clean and disinfect?
 - 4a. How often is it done?
- 5) When was last time each of the following were replaced:
 - 5a. Mask
 - 5b. PAP tubing
 - 5c. Filters
 - 5d. If not within 6 months, why not?
- 6) Have you experienced daytime sleepiness even though you are using your PAP?
- 7) Have you been told that you still snore while wearing the PAP?

Oxygen Questions:

The following questions should be asked during every communication with a participant who is currently prescribed oxygen.

“Alright, now let’s review your current use of oxygen. Please remember there are no right or wrong answers! We are here to help.”

- 1) Are you wearing your oxygen with the PAP?*
 - 1a. If so is it every night? How many hours?*
- 2) How often do clean and disinfect your oxygen humidifier (if you use one)
- 3) How often do you change your oxygen cannula?
- 4) If you are not wearing your oxygen as directed by your physician, why not?
- 5) Have you noticed that you are experiencing any changes in your ease of breathing?*

Baseline Data review:

“Thank you! Now, let’s review your baseline data [navigate to baseline data, ensure participant is also viewing baseline data]. As you can see, we have uploaded your last 30-days of CPAP data. We have included three variables, the ‘total time connected’ each evening which reflects the total amount of time your CPAP device was worn on a given night, your ‘Apnea Hypopnea Index’ as it was recorded each evening and we also have ‘total leakage’ or the amount of air leaking from your mask each evening, recorded as well. Let’s take a closer look at each and discuss what these might mean for you and let’s set goals for improvement where we can! [review each variable individually] [set goals relating to improving total time connected]”

“I know we can reach these goals together! If you would like to speak with one of the RT Coaches you can reach us by using the chat function in the portal [navigate to chat function and instruct participant to send a message to the RT group]. Ok, now I’ll say hello back! Great. If you need to reach us you can message online at any time.”

“Do you have any questions? [Answer all questions]”

“Lastly, I just want to reiterate that we are here to help. You have no reason to feel insecure with us, we are your friends. But, if you have any clinical emergencies please always remember to seek help from your healthcare providers or call 911.”

“Now I am going to fill out a communication form to record what we have discussed today. You will also receive a communication form to fill out.”

"Thank you for your time! The next scheduled RT coach calls will be when you complete Modules 5 & 6, so we may not call you for a little while. But, remember you can use the chat function to reach us anytime! I look forward to speaking with you soon."

Post-question Script:

"Thank you for taking the time to speak with me and share some of your current therapy habits. Now that we have discussed your currently uses of therapy, I am curious what you would like to see change? How would you like to improve your life, your therapy use? Some example would be to increase the use of your CPAP device or

Resource to disinfecting and common mark problems, as well as solutions:

http://www.aarc.org/wp-content/uploads/2014/04/pap_adherence.pdf

Peer Coach Scripts

Peer Coach Scripts

- 1) First Call: Portal Functions, When to call you Peer Coaches?, Journal entry, Module 1 Introductions, My Calendar
- 2) Voicemail
- 3) Check in's (i.e. changes in medications, prescriptions, travel plans, adverse events)
- 4) AE form
- 5) Outgoing call

Initial Call:

"Welcome to the O₂VERLAP Study...my name is {INSERT PEER HEALTH COACH NAME}. How are you today?"

"As a reminder, this call may be monitored and/or recorded for quality and training purposes."

"I look forward to being your peer health coach today." [insert personal statement which relates Peer Coach experiences to that of participant i.e. COPD diagnosis, appreciation for peer help, past clinical experience if any, reason for volunteering etc.]

"Would you please tell me a little bit about yourself and your motivations for joining this study?"

"The purpose of the COPD Foundation's Information Line is to provide information and referrals to educate, empower, and engage the COPD community in order to improve their lives with COPD."

"As we begin exploring the online study portal, please remember that throughout this process we are here to help you along the way. When you begin the online study courses, you will be reviewing information about COPD and obstructive sleep apnea. You may already know some of the information being presented to you, but some information may be new. Regardless of whether information is new or old, you may call a Peer Health Coach anytime Monday through Friday from 9am to 6pm Eastern to ask questions and get answers!"

"Alright, let's log into the portal and explore some of the basic functions you may use to communicate with our Peer Health Coaches."

[Assist participant login if necessary, instruct on what URL to visit, how to change password etc. , however participant should be logged in at this point already because they will have been on the phone with a CRC just before connecting to speak with a peer coach— COPDF will add troubleshooting steps here once portal is finalized]

[COPDF to add instructions on how to chat with peer Coach via portal here]

"Now, let's test it out together. Please send me a message saying 'hello' and I'll reply!"

“Great! This online chat function is another way you may communicate with a Peer Health Coach. We will not see these messages automatically, but our Team will check the portal daily and should get back to you within 24 hours. However, please remember you may also call us Monday through Friday from 9am to 6pm Eastern. The chat function is great for questions you may have if you are reviewing materials outside of business hours or if you prefer not to chat on the telephone, but we encourage you to please call in and speak with someone anytime you have a question.”

“Alright, now, let’s fill out a Journal entry together! I’ll help you get there, let me know if you have any questions [Instructions on how to navigate to Journal]. Ok, so, we hope you’ll fill this journal out as often as possible. It would be helpful for you to fill it out daily so we can check in to see how you are feeling. The Journal will always ask you for the date and time. Please fill that out [wait a moment]. Great! Now, let’s move on to the symptoms check-in, please review what the symptoms for a Green, Yellow and Red Day are... which type of day are you having? If you are having a Green Day, great! You may sometimes have a yellow or red day; on yellow days please take the actions written to the right of the yellow day, please also be sure to report this to your healthcare provider at your next visit! It’s important to let your provider know how you’re feeling, it could be the onset of a cold or an exacerbation. If you are having a Red day, please call 911 immediately. Seek help. The study team is here for peer-support, but we cannot be relied on when you need clinical help. If you are having a red day, always call 911 and seek help! ”

“Do you have any questions?” [Answer questions]

“Alright, now let’s fill out the remaining questions in the Journal. We would like you to rate your quality of life, activity level, stress, mood, sleep satisfaction, confidence leaving the home and ‘How are you breathing today?’. We ask that you rate these from one to ten, one being that you are not satisfied at all and ten means that you are completely satisfied. Ok, please fill these out. Let me know when you are done! [Pause to allow for completion.] Great! Ok, now let’s hit submit.”

“The portal is going to log all of your responses to the Journal, so you will be able to look at your progress over time! Let’s look at that now... [Navigate participant to the graphs showing their Journal history. Confirm that the participant is also viewing the Journal entry graphs.] Alright, now that you can see the results, which of these are most important to you? What do you hope to see improve over time? [goal setting]”

“Anytime we speak with you we will ask you the following four things:”

- 1) Have you had any adverse events since we last spoke?
- 2) Have you had any changes in your oxygen prescription since we last spoke? Have you had any changes in your PAP prescription since we last spoke?
- 3) Do you have any travel plans, even for just a short weekend road trip?
- 4) How are you doing today? We want to help, if we can.

“Do you have any questions about when to call a Peer Health Coach or how to get into contact with a Peer Health Coach?”

"Thank you for your time today and we encourage you to get started on your coursework at your earliest convenience."

Voicemail Script:

"Hello, this is {INSERT PEER HEALTH COACH NAME} and I'm calling from the COPD Foundation's Information Line for [first name only, of participant]. This call is regarding the O₂VERLAP study. Please feel free to contact us for more information toll-free at [contact]. We are available Monday through Friday from 9am to 9pm Eastern (except holidays)."

Adverse Event, Questions to ask on each call:

- 1) Have you had any adverse events since we last spoke?
- 2) Have you had any changes in your oxygen prescription since we last spoke? Have you had any changes in your PAP prescription since we last spoke?
- 3) Do you have any travel plans, even for just a short weekend road trip?
- 4) How are you doing today? We want to help, if we can.

Outgoing Call:

"Hello, this is {INSERT PEER HEALTH COACH NAME} and I'm calling from the COPD Foundation's Information Line regarding the O₂VERLAP Study. May I speak with {INSERT PATIENT NAME}?"

"As a reminder, this call may be monitored and/or recorded for quality and training purposes."

My Calendar:

"Alright, now that we have gotten that squared away lets go to your dashboard to view your My Calendar application. Enter the date you started Module 1 Lesson 1. Once you do this you should see seven square which represent each curriculum module. The date which that Module should be completed by, or the due date, will be directly under the square. This is great to reference as you are trying to determine how to budget time for the week. We hope you will find this helpful!"

Journal:

"Alright, now, lets navigate to our journal. You will notice that the top of the screen asks you to enter the date and time, please [participants name] enter your name and date. After that point you are ready to report how well you feel on a given day as it relates to your Quality of Life, Activity Level, Stress, Mood, Sleep Satisfaction, Confidence leaving the home and How are you breathing today. Over time, your responses to these items will be logged in a graph displayed in your Insights section of the dashboard.

Do you see your entry in the insights section now? [Pause for response....]

Excellent!

Do you have any questions?"

